3.9 Software

The standard software program R (v 3.5 or higher, R Foundation for Statistical Computing, Vienna, Austria) will be used for all descriptive and inferential analyses.

4 Analysis Populations

4.1 Summary

The following analysis populations are planned for this study:

- The **screening population**, which includes all patients who are screened for participation in the trial.
- The **safety population**, which includes all patients who received the intervention.
- The **intent-to-treat efficacy population**, which includes all patients who are randomized.
- The **per-protocol efficacy population**, which includes all patients in the intent-to-treat efficacy population, excluding patients with any of the following:
 1. Major protocol deviations, or 2. Noncompliance with study medications (more than 20% of the treatment missed).

4.2 Major protocol deviations

The incidence of deviations from the inclusion and exclusion criteria will be summarized using counts and percentages, and the treatment groups compared for the overall frequency of deviations using a 2xN Fisher's exact test. Similar deviations will be grouped into general categories of deviations for a more condensed summary. A listing of deviations by participant will also be produced. Any major deviations from the protocol will be listed and/or summarized, including, but not limited to, participants who:

- Never received treatment,
- Were subsequently found to be ineligible for the study,
- Never returned for a follow-up visit,
- Have follow-up visits outside the prescribed visit window.

The number and percentage of randomized participants actually receiving the study intervention and permanently discontinuing the study interventions will be summarized. A summary of study participants randomized by site will also be provided. Randomization groups will be compared for the proportion and reason for study intervention discontinuation using the Fisher's Exact test. A summary of participant status at the end

of the study period will also be generated with categories including lost to follow-up.

5 Data Collection and Quality Assurance

5.1 Quality assurance and security

Data collection forms, training, security, and quality assurance are discussed in the Manual of Operations.²

5.2 Analysis sets

Data sets for analysis will be produced at the Proctor Coordinating Center by the Data Analysis Committee. Each will be a CSV file containing a single header line whose variable names match the REDCap database. Each column will be a different variable. Each row will be a different observation. Character strings will be used whenever possible. Missing values will be coded as NA. Checks will be made to ensure that each variable in the analysis set has in-range values.

A detailed codebook will be prepared, containing for each variable, (a) the form from which the variable is derived, (b) text of the question, (c) all possible values for the variable, and (d) summary statistics for the variable. Note that all codes and character strings that represent categorical factors will be clearly defined. Units for each continuous variable will be indicated for each variable. Each release of the analysis set will be accompanied by the corresponding version of the codebook.

5.3 Data monitoring reports

Data monitoring reports will be prepared based on analysis data sets. The monitoring reports will include recruitment reports for each site, compliance reports, retention reports and data quality reports. These will be reviewed at the central site on a monthly basis and communicated to the study sites on a monthly basis.

6 Human Subjects

6.1 Summary of final dispositions

All subjects who provide informed consent will be accounted for in this study. The frequency of subjects in each population will be presented. We will also present the frequency of subjects in each subgroup, the frequency of withdrawal and loss to follow-up and any major protocol violations.

6.2 Data and Safety Monitoring Committee

6.2.1 Scope

The DSMC will be appointed by the NEI. We propose that this committee consist of 5-7 individuals, and should include uveitis specialists, a rheumatologist, a trialist, an independent biostatistician, and a bioethicist. The NEI Program Official serves as a resource to the DSMC but is not on the DSMC, does not vote, attends the open sessions, and may attend the closed sessions when deemed necessary by the Chair of the DSMC. The committee will meet in person at least once in Year 01 and 05. Other meetings may be arranged. All study protocols will be subject to review and approval by the Institutional Review Board at UCSF (central IRB for US sites), the South Central Berkshire Research Ethics Committee, the ethics committee at Melbourne, and by the DSMC.

6.2.2 Meetings

All in-person and teleconference meetings of the DSMC and study personnel will consist of (a) “open” sessions, which may be attended as needed by masked study personnel, and (b) “closed” sessions attended by only unmasked study personnel and (c) “closed” sessions attended only by the DSMC personnel. Care will be taken so that no intervention assignments, or data which would allow intervention assignments to be determined will be revealed during the open sessions.

The DSMC will be unmasked. Closed reports will tabulate baseline covariates, adverse events, and outcomes by treatment assignment and study site. Written closed reports will always use the labels Treatment A and Treatment B for increased information security. However, the DSMC will know which drug corresponds to which label.

The Coordinating Center’s biostatistician will determine the database closure dates for each report in advance; archival copies of the (a) main REDCap database, and (b) study analysis file as they exist at the time of each report will be maintained.

Interim reports for the DSMC will be prepared by the Proctor Coordinating Center. These reports will include (a) recruitment overall, and by study site, (b) compliance and (c) retention. The reports will also list study outcomes and all adverse outcomes, including deaths.

All reports will be sent using secure email to the members of the DSMC at least one week prior to each meeting.

Each printed (hard copy) interim report will be labeled clearly as confidential, bound so that the contents are not visible from the outside, and labeled with the name of each person authorized to receive it. Reports will be kept in possession of the primary biostatistician and research data analyst and only delivered in person or by encrypted email; reports not delivered due to absences are to be shredded. In addition, redacted versions of the interim reports will be prepared which contain no masked study information, and which are suitable for restricted distribution to other personnel on an as-needed basis. All hard copies will be destroyed at the end of each meeting, except for a copy to be kept in a locked file cabinet accessible only to the research data analyst.

6.2.3 Decisions

The DSMC will not make decisions about the trial, but rather advise the NEI and the Executive Committee of ADJUST as to whether a protocol should continue as scheduled or undergo a modification (details specified in the DSMC charter, section 5.5). The DSMC will make recommendations with the benefit of prespecified decision guidelines. Interim stopping guidelines for efficacy, futility, and safety are described above, in section 3.7 of the SAP. The DSMC will monitor safety data throughout the trial and will have the full support of the unmasked team at the trial's Data Coordinating Center to provide additional details on patient status or outcomes should that be needed to inform a recommendation to NEI and ADJUST Executive Committee.

7 Safety and tolerability

The analysis of safety in this study will include summaries of the following:

- Exposure
- Adverse events
 - Non-serious and serious ocular and non-ocular adverse events
 - Adverse events leading to withdrawal from the study, and from the drug
 - Any deaths

7.1 Exposure

Individuals are assumed to have exposure to the intervention corresponding to the group to which they were randomized.

7.2 Adverse Events

7.2.1 Individual Events

Adverse event reporting procedures are described fully in Protocol Section 8.3.² Non-serious adverse events are described in Protocol Section 8.3.1.² Serious non-ocular or ocular adverse events (which must be reported within 24 hours and which require a narrative form) are described in Protocol Section 8.3.2.² Adverse events will be reported in all presentations and publications.

Safety-related events that occurred at or before treatment failure with censoring at 6 months and then 12 months (two different groups of safety-related events) will be tabulated and reported. Descriptive tables of the number and frequency of adverse events will be broken down by treatment group, age, sex, antimetabolite use and known comorbidities. We will report total adverse events and serious adverse events, cross-tabulated by whether the adverse events were anticipated or unanticipated and by whether or not the adverse event led to discontinuation of medication.

We do not propose statistical evaluation of adverse events, since the study is not powered for such assessments.

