Discontinuation due to *intolerability*: Patients may discontinue their current treatment regimen due to side effects. Once side effects resolve, patients may restart their treatment regimen. Discontinuation for intolerance is NOT a treatment failure. Patients should still complete all study visits through Month 12.

Discontinuation due to *safety*: Patients who experience abnormal lab results meeting the designated threshold of an AE or other AEs such as an opportunistic infection will immediately stop taking both the study treatment and concomitant antimetabolite therapy if applicable. These AEs are often reversible. In the case of non-serious and serious lab AEs, patients may restart medication when the lab results have normalized. Discontinuation for safety reasons is NOT a treatment failure. Patients should still complete all study visits through Month 12. Patients who develop an illness, such as a febrile illness, $\geq 101^{\circ}\text{F}/38.3^{\circ}\text{C}$ or an infection requiring antibiotics, should consult their study physician regarding treatment and may stop taking the study medication and antimetabolite per investigator's discretion. Under the discretion of the investigator, patients should resume treatment as soon as it is determined to be safe. Note, patients should not stop treatment due to milder illnesses such as upper respiratory infections (colds). Additionally, patients who develop any of the following will also discontinue treatment according to the full prescribing information and labeling in the SmPC: serious infections,

opportunistic infections (including invasive fungal infections) or sepsis, Hepatitis B reactivation, new or worsening symptoms of congestive heart failure, or central or peripheral nervous system demyelinating disorders. If the investigator determines it is safe for the patient to restart treatment upon resolution of the disorder, the patient will restart.

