8.3 ADVERSE EVENTS AND SERIOUS ADVERSE EVENTS

8.3.1 DEFINITION OF ADVERSE EVENTS (AE)

Adverse event means any untoward medical occurrence associated with the use of an intervention in humans, whether or not considered intervention-related (21 CFR 312.32 (a)).

Examples* may include:

- Increased intraocular pressure (>24 mm Hg)
- Abnormal lab findings (≥ 2 times but < 5 times the upper limit of normal AST or ALT, rise in creatinine to ≥ 1.5 to < 2 mg/dL, reduction of white blood cell count to below 2500)
- Concurrent accident or illness
- Increase in the frequency and severity of symptoms of a pre-existing condition
- Side effects such as gastrointestinal upset, nausea, vomiting, fatigue

*Additional details on adverse event reporting are provided in the case report form: **Adverse Event Checklist**.

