8.3.4 TIME PERIOD AND FREQUENCY FOR EVENT ASSESSMENT AND FOLLOW-UP

The occurrence of an AE or SAE (encompassing serious adverse reactions, SARs, and suspected unexpected serious adverse reactions, SUSARs, in the UK) may come to the attention of study personnel during study visits and interviews of a study participant presenting for medical care, or upon review by a study monitor.

All AEs including local and systemic reactions will be captured on **Adverse Event Checklist**. All AEs that occur during the study must be documented appropriately regardless of relationship and will be categorized as either serious or non-serious. All AEs will be followed to adequate resolution.

Any medical condition present at the time that the participant is screened will be considered as baseline and not reported as an AE. However, if the study participant's condition deteriorates at any time during the study, it will be recorded as an AE.

The study coordinator will record all reportable events with start dates occurring any time after informed consent is obtained until 70 days after the last day of study participation and the last dose of study medication. At each study visit, the study coordinator will ask about the occurrence of AE/SAEs

since the last visit. Events will be recorded on **Adverse Event Checklist** at each visit and followed for outcome information until resolution or stabilization.

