10.1.12.5 TRIAL SAFETY

A masked medical monitor at the CC has been appointed to evaluate the safety of the trial. All serious adverse events experienced by enrolled patients will be reported to the medical monitor in a timely manner, as defined in section 8.3.6. The medical monitor will determine expectedness of the patient's treatment and the reported event. The medical monitor will report his findings to the relevant entities defined in section 8.3.6.

The NEI's appointed DSMC will also review serious adverse events and general trial data on a 6-month basis, or as deemed necessary. Progress reports will be prepared for all scheduled DSMC meetings. An interim analysis will be performed and presented to the DSMC by the trial's unmasked biostatistician when approximately 40% of the trial's anticipated events have occurred. Whether or not to continue the trial will be based on this interim analysis. See **SAP section 3.7** for details on stopping.

On February 14th, 2024 the DSMC met, stopped enrollment and provided the following guidance for patients still completing follow-up in the trial:

- Patients should be told by the study investigator the results regarding efficacy of the continued administration of adalimumab for preventing recurrence of uveitis or arthritis.
- Patients are encouraged to remain in their assigned treatment group and complete follow-up, per protocol.
- Patients in active follow-up who have not yet been unmasked to their treatment assignment can be asked if they want to know their current treatment assignment.
- Patients receiving placebo may opt to discontinue their injections.

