7.2.2 Pooled adverse events

Adverse events will be analyzed according to six main categories:

- Proportion of subjects with any ocular adverse event
- Proportion of subjects with any ocular serious adverse event
- Proportion of subjects with any systemic adverse event
- Proportion of subjects with any systemic serious adverse event
- Proportion of subjects with any laboratory adverse events
- Proportion of subjects with any laboratory serious adverse events

Note, hypothesis tests based on adverse events may be less than useful because the trial is not powered for these comparisons. These will only be provided to the DSMC if requested.

8 Reporting conventions

- All tables, data listings and figures will be presented in landscape orientation
- Direct annotation of figures will be preferred to legends. All figures with more than one variable or item will contain direct annotation
- Color will be used in figures only when needed to enhance clarity of communication

9 Appendix

All computations will be performed using the R statistical software ([R Core Team 2021](#)).³⁹ Specification of the random number seed and pseudorandom number algorithm determines the entire randomization assignment. Accordingly, the random number seed will be kept confidential.

10 References

2. [name]. *Adalimumab in Juvenile Idiopathic Arthritis-Associated Uveitis Stopping Trial (ADJUST)*.; 2019.

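### The SAP's adverse-event tables stop at treatment failure and give no time at risk, so equal rates of events unrelated to recurrence would show as more events on continued adalimumab

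*SAP*

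**What the plan says.** - SAP 7.2.1 limits one tabulation to "Safety-related events that occurred at or before treatment failure with censoring at 6 months and then 12 months". It goes on: "Descriptive tables of the number and frequency of adverse events will be broken down by treatment group, age, sex, antimetabolite use and known comorbidities". That sentence and the one after it, on total and serious events, do not repeat the pre-failure limit. The section gives no denominator in time and proposes no statistical evaluation.
- SAP 7 lists exposure among the safety summaries, but 7.1 says only: "Individuals are assumed to have exposure to the intervention corresponding to the group to which they were randomized". It mentions neither duration nor doses.
- SAP 7.2.2 lists six proportions, such as "Proportion of subjects with any systemic adverse event", across ocular, systemic and laboratory categories. It states no window.
- Protocol 4.1 hypothesises a higher adverse-event rate on continuation and says that rates will be compared between the arms.
- Protocol 8.3.1 gives as an example of an adverse event "Increase in the frequency and severity of symptoms of a pre-existing condition". Protocol 8.3.4 says that if a participant's "condition deteriorates at any time during the study, it will be recorded as an AE".
- Protocol 7.1 states: "Discontinuation for safety reasons is NOT a treatment failure". Protocol 10.1.12.5 adds, for the period after 14 February 2024: "Patients receiving placebo may opt to discontinue their injections".

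**The concern.** Where the pre-failure limit applies, a patient stops contributing adverse events on reaching the primary endpoint. The trial expects that endpoint sooner in the stopping arm, so the two arms are observed for different lengths of time because of the treatment effect itself. Without a time denominator, a by-arm table of counts mixes the rate of harm with the length of observation.

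The documents are also not aligned: the protocol speaks of adverse-event rates, while the SAP supplies no time from which to form one.

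Pre-failure time is not time on study drug either. Stopping for safety or intolerance is not a failure. Placebo patients could stop injections after the interim decision. Protocol 3.1 dates an ocular failure back to the first visit at which the threshold was reached. Exposure defined as the randomised arm captures none of this.

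At stake is how a published safety table is read when the harms of continuing are weighed against the risk of stopping.

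**Working it through.** **Inputs.** From SAP 3.3.1: median time to failure 10 weeks (stopping) and 20 weeks (continuing), 59 per arm, 10% loss, two-sided alpha 0.05. From the protocol's visit schedule: Month 12 is week 48 and Month 6 is week 24. Failure times are taken as exponential, as in the SAP's formula. The documents give no adverse-event rate, so any rate below is an assumption.

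**Check of the plan's own figure.** Let L = ln 2 / median, giving 0.06931 and 0.03466 per week. With T = 48, the SAP's function L²/(1 − exp(−LT)) is 0.004983 and 0.001482. Then n per arm = (1.960 + 1.175)² × 0.006465 / 0.03466² = 52.9, so 53 per arm and 106 in total. Dividing by 0.9 gives 117.8, or 118. The stated 118 patients at 88% power are reproduced.

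**Length of the pre-failure window.** Mean time to failure or cut-off = (1 − exp(−LT))/L.

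| Cut-off | Stopping | Continuing | Ratio |
|---|---|---|---|
| 48 weeks | 0.9641/0.06931 = 13.9 weeks | 0.8105/0.03466 = 23.4 weeks | 1.68 |
| 24 weeks | 0.8105/0.06931 = 11.7 weeks | 0.5647/0.03466 = 16.3 weeks | 1.39 |

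If unrelated events occur at the same constant rate in both arms, expected counts are proportional to these windows. The ratio of counts therefore equals the ratio of windows, whatever the rate.

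**Range at 48 weeks.**
- 8 vs 16 weeks (SAP Table 4): 20.2/11.4 = 1.78.
- 12 vs 24 weeks (SAP Table 4): 26.0/16.2 = 1.60.
- 100 days (SAP Table 3) vs 20 weeks: 23.4/18.6 = 1.26.
- 10 weeks vs the long-term figures in SAP 3.3.1: 90% inactive at week 54 gives L = −ln(0.90)/54 = 0.00195, a window of 45.8 weeks and a ratio of 3.3. Using 74% at week 78 gives L = 0.00386, 43.8 weeks and 3.2.
- Dating failure at the next scheduled visit instead of continuously lowers the 10 vs 20 week ratio to 25.9/16.6 = 1.56.

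**Patients with any unrelated event.** The proportion is r/(r + L) × (1 − exp(−(r + L)T)) for an assumed rate r per week. At 48 weeks:
- r = 0.01: 0.123 vs 0.198, ratio 1.60.
- r = 0.10: 0.590 vs 0.741, ratio 1.26.

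The distortion in proportions is smaller than in counts and shrinks as events become common.

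**If recurrences are coded as adverse events.** By week 48 the failure itself would add up to 0.96 events per patient on stopping and 0.81 on continuing, which pulls the other way. Patient-time does not remove this component, because the design hazard ratio for failure is 2.0. Recurrence events therefore have to be shown apart.

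**If a table covers all follow-up.** Observation time is then about equal by arm, but 1 − 13.9/48 = 71% of stopping-arm time falls after failure. If everyone who fails restarts adalimumab (an assumption), a true on-drug rate ratio of 2.0 would appear as 2/(0.29 + 0.71 × 2) = 1.17.

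**The case against.** The strongest reply is that adverse events are explicitly descriptive and untested, so nothing inferential can go wrong. That stands, and it is why the point is minor. A descriptive table can still mislead.

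A second reply is that the wording leaves room. The term frequency does not exclude rates, and the sentences after the pre-failure limit could be read as covering all follow-up. This also stands in part. The ratios above apply only where the pre-failure window applies, and they do not apply to 7.2.2 unless its window stops at failure. But no reading supplies patient-time.

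A third reply is that other parts of the SAP help. Section 4.2 summarises receipt and discontinuation of the intervention by arm. Aim 3 reports several outcomes, including arthritis flare and discontinuations, regardless of failure. Reports to the monitoring committee tabulate adverse events by arm. None of these gives time at risk, and Aim 3 does not cover adverse events in general.

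A reader might go further and infer that the by-arm comparison cannot be interpreted in either direction. The documents do not support that:
- For events unrelated to recurrence, the direction is known. Equal or fewer such events on continuation would still be informative.
- A reversal requires recurrences to be coded as adverse events. Protocol 8.3.1 and 8.3.4 permit this, but the Adverse Event Checklist that would settle it is not in the documents.
- The split in SAP 7 and 7.2.2 confines any reversal. Uveitis recurrences would fall in the ocular category and in pooled totals, and arthritis recurrences in the systemic category to a lesser extent. Laboratory events would be untouched.

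**Conclusion.** The concern holds as a minor one. Where SAP 7.2.1's pre-failure window applies, equal true rates of events unrelated to recurrence would be expected to show more events on continuation. The count ratio is about 1.7 at 48 weeks and 1.4 at 24 weeks on the planning medians. At 48 weeks it runs from 1.26 to 1.78 across the SAP's other planning inputs, and is about 3.2 to 3.3 if continuation failures follow the long-term figures the SAP cites. For the proportion of patients with any event, the 48-week ratio is 1.60 to 1.26 at assumed rates of 0.01 to 0.10 per week.

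Because this leans the same way as the protocol's hypothesis, an excess on continuation cannot be attributed to the drug without patient-time.

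The figures rest on exponential failure times and on a constant unrelated-event rate that is equal in both arms and independent of failure. Whether recurrences are coded as adverse events remains unknown, and so does the window of 7.2.2. No hypothesis test or error rate is affected.

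**What to change.** - **SAP 7.1:** summarise by arm the patient-time to failure or censoring and, separately, the time actually on study drug.
- **SAP 7.2.1:** state which window each by-arm table uses. Report events per patient-year beside the counts, with no test. Show events that are the uveitis or arthritis recurrence itself separately from all other adverse events.
- **SAP 7.2.2:** state the window of the six proportions.
- **One added table:** all follow-up by randomised arm, descriptive, with patient-time and with post-failure events shown separately.

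The cost is a few columns, one table, a rule for flagging recurrence events, and some SAP wording. Event start dates, failure dates and medication logs are already collected. There are two limits: events per patient-year assume a roughly constant event hazard, and time on drug rests on self-reported adherence (Protocol 6.4).
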